### **10.2 Sample Size**

The proposed study is designed to collect performance data associated with CI532 cochlear implantation. Based on the preliminary data collected in IDE G120234, assuming the observed mean and standard deviation for each

---

CONFIDENTIAL

March 31, 2016

CAM-CL-027\_PRT

Rev. 1

Page 17 of 21

endpoint are representative of the corresponding values for the population, it was determined that a minimum of 23 evaluable subjects would provide at least 90% power for a hypothesis test of superiority at the one-sided 0.025 alpha level. Allowance of 10% to account for possible attrition brings the sample size to a minimum of 25 subjects to be recruited into the study and implanted. In effort to enroll subjects 12 years and under who are unable to complete speech perception for primary endpoint testing and have more than 3 subjects per site, the sample size has been increased to up to 50 subjects.

The following general assumptions have been made:

- Paired t-tests
- One-sided 0.025 or 0.05 alpha levels
- Assumed distribution for population (mean, SD) based on IDE G120234
- Desire for 80% or 90% power

Power for the primary test metric AzBio Sentences in SWN under a variety of assumptions is provided below.

Scenario	Minimum Evaluable Sample Size
One-sided 0.025 alpha, 80% power	18
One-sided 0.025 alpha, 90% power	23
One-sided 0.05 alpha, 80% power	16
One-sided 0.05 alpha, 90% power	20

Subject enrollment is estimated to take six months to recruit up to 50 subjects. The enrollment period may be extended if required.

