## **10. Data Analysis**

### **10.1 Statistical Analysis**

All subjects who are consented into the clinical study will constitute the intention-to-treat (ITT) population for the purposes of safety evaluation. Only subjects implanted with the CI532 and completed per the protocol will be considered as the completed cases (CC) population and per protocol (PP).

Demographic and outcomes data will be tabulated individually along with group summary descriptive statistics. Speech perception scores will be presented for each study evaluation, pre- and postoperatively, so that postoperative progress can be evaluated over time.

Performance with the Nucleus CI532 will be determined by a comparison of preoperative, best aided, ear to be implanted vs. 3 months postactivation outcome measures. The speech perception measures chosen for this purpose are the AzBio sentences in both quiet and noise in the unilateral listening condition.

The primary study endpoints will be statistically significant differences between the mean, preoperative speech perception scores and postoperative scores for the activated, CI532 cochlear implant subjects who completed speech perception testing. Mean scores as measured by AzBio sentences in quiet and noise will be compared. The null hypothesis to be tested is that there is no difference for the subjects between their pre- vs. postoperative speech performance

Individual scores obtained at 3 months will be compared with those obtained, on the same measures preoperatively, based on the binomial model where appropriate (see Thornton and Raffin, 1978; Boothroyd and Nittrouer, 1988). Although the binomial model is the more appropriate statistical model for analysis of single-subject experimental data, conventional group-based statistics will also be applied to the pooled results. For all of the speech perception measures, nonparametric procedures (e.g., a Signed-Ranks test) will be conducted in order to further confirm the results of the single-subject analyses. These tests will be two-tailed and applied using an alpha level of 0.05.

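### Do the table rows of 16 and 20 subjects, which do not fit the rows of 18 and 23, undermine the planned sample size?

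*Protocol*

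**What the plan says.** Section 10.2 of the protocol sizes the study on the statement that "a minimum of 23 evaluable subjects would provide at least 90% power" for a superiority test at one-sided 0.025. It then lists its general assumptions, including "Paired t-tests" and "Assumed distribution for population (mean, SD) based on IDE G120234", and introduces the table with "Power for the primary test metric AzBio Sentences in SWN under a variety of assumptions is provided below". The four rows are:

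| Alpha (one-sided) | Power | Printed minimum |
|---|---|---|
| 0.025 | 80% | 18 |
| 0.025 | 90% | 23 |
| 0.05 | 80% | 16 |
| 0.05 | 90% | 20 |

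The two rows in question are those labelled "One-sided 0.05 alpha, 80% power" and "One-sided 0.05 alpha, 90% power". The design uses the row labelled "One-sided 0.025 alpha, 90% power". After an attrition allowance, the recruitment minimum is 25. The ceiling is then raised to 50, partly to take in younger children who cannot do the speech tests. Section 10.1 tests at a two-tailed 0.05 level and adds that "nonparametric procedures (e.g., a Signed-Ranks test) will be conducted" on the speech measures. Neither the protocol nor the SAP gives a numerical mean, SD or effect size.

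**The concern.** The table is described as one endpoint, one test and one assumed distribution, with only alpha and power varying. One standardised change (mean paired difference divided by its SD) should therefore generate all four minima. If none does, at least one row was not produced as described, and the reader cannot tell which, because the mean and SD are only referenced to an earlier study.

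What would be at stake is the 90% power claimed for 23 subjects. If the true planning assumption sat behind one of the 0.05 rows, the effect size would be smaller than the 0.025 rows imply, and 23 subjects would have less than 90% power.

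**Working it through.** **Inputs.** From section 10.2: paired t-test, one-sided alpha 0.025 or 0.05, power 80% or 90%, printed minima 18, 23, 16 and 20. The standardised change d is not given, so it is solved for.

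**Formula.** For n pairs, power = P(T > t(1−α, n−1)), where T is noncentral t with n−1 degrees of freedom and noncentrality d√n. The minimum n is the smallest one that reaches the target power.

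**Step 1: which d makes each printed number the exact minimum?**

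| Row | Printed n | Range of d |
|---|---|---|
| 0.025, 80% | 18 | 0.7007 to 0.7239 |
| 0.025, 90% | 23 | 0.7075 to 0.7250 |
| 0.05, 80% | 16 | 0.6517 to 0.6755 |
| 0.05, 90% | 20 | 0.6792 to 0.6983 |

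The first two ranges overlap at 0.7075 to 0.7239, so 18 and 23 are reproduced together. Neither 0.05 range reaches that overlap, and the two 0.05 ranges do not meet each other.

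**Step 2: what should the 0.05 rows be if the 0.025 rows are right?**

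- At d = 0.7075 the four minima are 18, 23, 14 and 19.
- At d = 0.7238 they are 18, 23, 14 and 18.

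So 16 exceeds the exact minimum by 2, and 20 exceeds it by 1 or 2. At one-sided 0.05 over this range, 16 subjects give 85.4% to 86.8% power (labelled 80%) and 20 give 92.0% to 93.0% (labelled 90%). Both rows over-deliver.

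**Step 3: the design row.** Over the same range, 23 subjects at one-sided 0.025 give 90.0% to 91.2% power, as section 10.2 claims. One-sided 0.025 is the efficacy side of the two-tailed 0.05 test in section 10.1, so sizing and analysis match.

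**Step 4: how large is the misfit?** For d from about 0.6915 to 0.702, every row is within one subject of its printed value.

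**Step 5: could another convention explain the table?** A plain normal approximation does not give the set exactly, and neither does a simulated exact signed-rank test on normal differences over a grid of d. The signed-rank test comes closest at d = 0.73, with 18, 23, 15 and 19. A normal approximation plus a fixed allowance does give it. With d = 0.78 (d² = 0.6084) and n = (z₁₋α + z_power)²/d², rounded up, plus 5:

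- 7.849/0.6084 = 12.90, so 13 + 5 = 18
- 10.507/0.6084 = 17.27, so 18 + 5 = 23
- 6.183/0.6084 = 10.16, so 11 + 5 = 16
- 8.564/0.6084 = 14.08, so 15 + 5 = 20

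Allowances of 4 and 6 also work, each at its own d. Nothing shows that the sponsor did this. It shows only that an unstated convention cannot be excluded.

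**The case for a change.** The strongest case for acting is that the column claims to give minimum sizes, which are exact integers from shared inputs, so rounding of an unstated d cannot explain a set that no d produces. The table is also the only numerical support for the 90% claim. If the row of 16 carried the true assumption, power at 23 would be 84.8% to 87.2%; if the row of 20 did, 87.5% to 89.2%. At the d that fits all four rows best, the design row would be 24, with 88.7% to 89.6% power at 23. Writing down two numbers and recomputing four is about an hour's work.

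Much of this stands. As described, the table does not cohere under an exact paired t-test, and 23 cannot be verified from first principles. What does not stand is the step to a threat to the design. The lower power figures need an unused row to hold the true effect and the row the sponsor chose to be the wrong one, and nothing in the documents points that way. The two 0.025 rows support each other; the two 0.05 rows do not. Even in the least favourable case, the need would be about 26 or 27 evaluable subjects. That is below the ceiling of 50, although some of those places are meant for children who will not contribute to the endpoint.

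**Conclusion.** The mismatch is real but small, and it sits in rows that nothing depends on. If the 0.025 rows are taken as sound, 16 and 20 are one or two subjects above the exact minima of 14 and 18 or 19, so they err on the safe side. The design figure of 23 is consistent with its companion row, gives 90.0% to 91.2% power at the effect size the two rows share, and matches the level of the planned tests. It has not been shown to be wrong.

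The absent mean and SD are a reporting gap. Supplying them would let a reader confirm 23 directly, and the two illustrative rows could be corrected or explained in passing. Neither step would alter the recruitment target, the test, the alpha level or how the results are read, so there is no gain that calls for a change to the plan.

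This rests on two assumptions: that the 0.025 rows reflect the planning effect size, and that they came from a paired t-test, as section 10.2 states.

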## 11. Risk Benefit Statement

### 11.1 Benefits

It is possible but not guaranteed that advances to cochlear implant technology will improve performance or usability of devices for future recipients. This investigation will help to inform the future development of potentially new electrode designs and the planning of future studies in the newly implanted population. There are no direct benefits anticipated for subjects participating in this study.

---

CONFIDENTIAL

March 31, 2016

CAM-CL-027\_PRT

Rev. 1

Page 18 of 21

## **11.2 Risks**

It is expected that the risks associated with the procedure to place the cochlear implant are no greater than those associated with cochlear implantation in general. Cochlear implantation is an accepted treatment option for adults with bilateral moderate (for low frequencies) to profound sensorineural hearing loss.

With any cochlear implant mapping, there is a very small risk of unintentional over-stimulation. Subjects may experience sounds during mapping that are uncomfortably loud.

## **12. Good Clinical Practices Statement**

The study obligations for the Investigator(s) are outlined in guidelines for Good Clinical Practice (GCP), ISO14155:2011 (Clinical Investigation of Medical Devices for Human Subjects – Good Clinical Practice), and the Declaration of Helsinki.

## **13. Access to Study Documents and Study Monitoring**

Investigator(s) will provide access to study documentation including source data for the purposes of monitoring, audits, IRB review, and regulatory inspections.

## **14. Quality Control and Assurance**

Study sites may be subject to Quality audits at any point during the study. Regulatory agencies may conduct inspections during the course of the clinical investigation and after study completion.

## **15. Institutional Review Board**

Each site will obtain approval from its designated IRB prior to commencing any study-related activities. A copy of the IRB approval will be kept in the Investigator file(s). Any additional requirements imposed by the IRB and/or regulatory authority shall be followed. The Investigator(s) will submit the appropriate documentation if any necessary extension or renewal of the IRB approval must be obtained.

## **16. Informed Consent Process**

Written informed consent shall be obtained from each subject after explaining the rationale for and the details, aims, and objectives of the study, the risks and benefits of the trial treatment (and alternative treatments), and the extent of the patient's involvement. The Investigator is responsible for ensuring that all

---

CONFIDENTIAL

March 31, 2016

CAM-CL-027\_PRT

Rev. 1

Page 19 of 21

Cochlear

patients give written informed consent prior to any study-related examination or activity. All patients shall sign and date the Informed Consent Form, and a copy of the Informed Consent Form shall be given to the patient.

The Sponsor and the Investigator(s) shall avoid improper influence on or inducement of the subject, monitor, the Investigator(s) or other parties participating in or contributing to the clinical investigation.

## **17. Confidentiality**

A Case Report Form (CRF) will be completed for each study subject, summarizing all clinical and study data. The CRF contains confidential material. Subjects will only be referred to in the CRF by their subject numbers in order to retain subject confidentiality. Specific instructions to complete the CRF shall be provided to the clinical investigation team as appropriate.

Copies of the completed CRFs are to be provided to the Sponsor as soon as practical after completion and review. The original CRFs are to be retained by the Investigator for a period of time as determined by local regulations.

## **18. Protocol Deviations and Amendments**

The Investigator must receive prior approval from the Sponsor, and the IRB when necessary, to deviate from the protocol except in cases of emergency to protect the rights, safety, and well-being of the subjects. Emergency protocol deviations must be documented and reported to the Sponsor and the IRB.

Study procedures will not be changed without mutual agreement between the Sponsor and the Investigator(s). Changes will be implemented in a signed protocol amendment, and for significant changes, approval will be obtained from the IRB.

## **19. Data Management**

Data will be recorded on electronic CRFs within the electronic data capture system DataLabs™. DataLabs will produce a report of the summary data per subject. Source data for study evaluations may include paper worksheets or electronic spreadsheets. All source data will be stored in subject binders or on password-protected computers. The study monitor will compare the DataLabs CRFs with the source data.

---

CONFIDENTIAL

March 31, 2016

CAM-CL-027\_PRT

Rev. 1

Page 20 of 21

## 20. Record Keeping and Retention

All source documents, CRFs, and trial documentation will be kept by the Investigator(s) for the appropriate retention period as stipulated by local regulations and ICH-GCP.

## 21. Study Report and Publication

A description of this clinical trial will be available on <http://www.ClinicalTrials.gov>, as required by U.S. Law.

The aggregate data resulting from this study will be the proprietary information of the Sponsor and may be made public after all data have been analyzed and the study results are available. None of the data resulting from this study will be allowed to be presented or published in any form, by the Investigator or any other person, without the prior written approval of the Sponsor. At the end of the study, a clinical study report will be written by the study Investigators or their designee and reviewed by the Sponsor.

Implantation with the Cochlear Nucleus® CI532 Implant, Early Experience Study

NCT02755935

January 23, 2018

Section 10.1 of this study protocol stated that demographic and outcomes data would be tabulated individually along with group summary descriptive statistics. Speech perception scores were presented for each study evaluation, pre- and postoperatively, in order to evaluate postoperative progress over time.

The primary study endpoints were difference between the mean preoperative speech perception scores and postoperative scores for the activated, CI532 cochlear implant subjects who completed speech perception testing. Mean scores as measured by AzBio sentences in quiet and noise were compared. The null hypothesis tested was that there is no difference for the subjects between their pre- vs. postoperative speech performance

Individual scores obtained at 3 months will be compared with those obtained, on the same measures preoperatively, based on the binomial model where appropriate (see Thornton and Raffin, 1978; Boothroyd and Nittrouer, 1988).

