## 7. Investigational Procedures

### 7.1 Design Overview

The Implantation with the Cochlear Nucleus® CI532 Implant - Early Experience Study will be conducted as a multi-center, prospective, single-arm clinical study, evaluating the safety and functionality of the Cochlear Nucleus CI532 cochlear implant in up to 50 subjects who meet current cochlear implant indications. A single-subject repeated-measures analysis will be employed whereby subjects will act as their own control. A single-subject research design is appropriate since it accommodates the heterogeneity that characterizes hearing-impaired populations. Blinding procedures are not appropriate for this trial design, as it is not possible to conceal the presence, or absence, of a cochlear implant from device recipients and/or clinical investigators.

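### Does the SAP leave the mean-score endpoints without a test by keeping only the single-subject binomial comparison?

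*SAP*

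**What the plan says.** Protocol section 10.1 sets the criterion: "The primary study endpoints will be statistically significant differences between the mean, preoperative speech perception scores and postoperative scores". It then provides two levels of analysis. At the individual level, each subject's preoperative and 3-month scores are compared under the binomial model. The group level, which concerns the data pooled over subjects, is introduced with "Although the binomial model is the more appropriate statistical model for analysis of single-subject experimental data, conventional group-based statistics will also be applied". A further sentence adds that "nonparametric procedures (e.g., a Signed-Ranks test) will be conducted in order to further confirm the results of the single-subject analyses". The section closes with the level: "These tests will be two-tailed and applied using an alpha level of 0.05".

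Protocol section 10.2 sizes the study on paired t-tests: 23 evaluable subjects for at least 90% power at one-sided 0.025.

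The SAP, dated January 23, 2018, opens by citing section 10.1 and then follows it closely. Its endpoint sentence is "The primary study endpoints were difference between the mean preoperative speech perception scores and postoperative scores", without the significance wording. It says that mean AzBio scores in quiet and noise were compared, and continues: "The null hypothesis tested was that there is no difference for the subjects between their pre- vs. postoperative speech performance". Its last sentence is "Individual scores obtained at 3 months will be compared with those obtained, on the same measures preoperatively, based on the binomial model where appropriate". The three closing sentences of section 10.1, which carry the group statistics, the nonparametric tests, the sidedness and the alpha, do not appear.

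**The concern.** A SAP normally adds detail to the protocol. This one has less. A reader who opens only the SAP finds an endpoint about means, a null described as tested, and a single named method that returns a verdict for one subject at a time. No rule combines those verdicts, so the method cannot reject a null about a mean.

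The protocol also has wording that could seem to put the single-subject analysis first. Section 7.1 says "A single-subject repeated-measures analysis will be employed whereby subjects will act as their own control", and section 10.1 has the nonparametric tests confirming the single-subject results, when one would expect the group test to decide and the individual results to describe.

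If the deciding analysis were really open, the stakes would be real. Individual and group analyses answer different questions, and the SAP is written mostly in the past tense nearly two years after the protocol of March 31, 2016. A criterion chosen after the scores were seen would weaken the primary claim.

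**Working it through.** **1. Text comparison.**

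| Element | Protocol 10.1 | SAP |
|---|---|---|
| Endpoint | Significant difference in mean scores | Difference in mean scores |
| Comparison of group means | Yes | Yes, test not named |
| Null of no pre/post difference | Yes | Yes |
| Individual binomial comparison | Yes | Yes |
| Group statistics on pooled results | Yes | Not repeated |
| Signed-ranks test, as an example | Yes | Not repeated |
| Two-tailed, alpha 0.05 | Yes | Not repeated |

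Everything absent from the right-hand column stands in the middle column. The SAP contains no statement that withdraws or replaces section 10.1. It also does not offer the binomial comparison as the test of the mean endpoint: that sentence concerns individual scores and follows a separate statement that means were compared.

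**2. Can the binomial comparison stand in for a group test?** It cannot. If no subject changes and each is tested at 5%, the chance of at least one significant subject among 23 is 1 − 0.95^23 = 0.693. In a simulation with assumed list lengths of 20 to 140 items and baseline scores of 25% to 55%, a uniform gain of 6 points made 6% to 17% of subjects individually significant, while a paired t-test on the same 23 subjects rejected in 44% to 99.6% of trials. This shows that the two analyses differ. It does not show that the sponsor would use one for the other, because section 10.1 assigns the binomial model to single-subject data and group statistics to the pooled results.

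**3. Do the levels in 10.1 and 10.2 conflict?** A two-sided 0.05 test puts 0.025 in the upper tail, so its upper critical value is z = 1.960, the same as for one-sided 0.025. For a paired t-test with 22 degrees of freedom both give 2.074. The level in section 10.1 is therefore the level at which section 10.2 sets its 23 subjects. The one-sided 0.05 rows in 10.2 are alternative sizing scenarios.

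**4. What does the unnamed group test cost?** The documents give no mean or SD, so the effect size has to be worked back from section 10.2.

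- Formula: power = 1 − F(t_crit; df = n − 1, noncentrality = d√n), with F the noncentral t distribution.
- Reproducing the plan's figure: n = 23, one-sided 0.025 and at least 90% power require d from 0.7075 up to 0.725. At d = 0.7075 the noncentrality is 0.7075 × √23 = 3.393 and power is 90.0%; with 22 subjects it is 88.6%, so 23 is the minimum.
- Signed-ranks test at n = 23, d = 0.7075, two-sided 0.05, simulated with normal differences: about 88.4%.
- Difference: 90.0 − 88.4 = about 1.6 points from the rounded figures, so roughly 1.5 points.

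No single d reproduces all four rows of the 10.2 table. The rows imply values from 0.652 to 0.725, over which paired t-test power at n = 23 runs from 84.8% to 91.3% at one-sided 0.025. The table covers sentences in noise only, so these values say nothing direct about the quiet endpoint.

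**The case for a change.** The best case for a change is that the SAP cites section 10.1 only for tabulation and descriptive statistics, so it does not expressly carry the tests across. Even with 10.1 read in, the group test is not pinned down: 10.1 names signed-ranks as an example, and 10.2 assumes paired t-tests. A SAP exists to settle that, and nothing shows when the test was chosen relative to data access.

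Part of this stands. The SAP does not say which group test produced the primary result, and one sentence would have done so. The statement that nonparametric tests confirm the single-subject results is also awkward.

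Three things limit it. First, citing a section for one purpose does not revoke the rest of it, so a result can still be checked against the criterion and level in 10.1. Second, the section 7.1 wording on subjects as their own control fits the within-subject, repeated-measures design of section 3 and can simply mean paired analysis, which both group tests satisfy. Third, a significant mean change alongside a minority of individually significant improvers is no contradiction, since these are complementary summaries. Any estimate of how often that happens depends on baseline scores, spread and item counts that the documents do not give, and any majority rule for individual results would have to be invented.

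Making the t-test decisive would also demote the only test that 10.1 names, for a small gain in power.

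**Conclusion.** The omission is real, but it is a gap that an analyst holding both documents would fill sensibly. The natural reading is a paired group comparison of preoperative and 3-month AzBio scores for each endpoint, two-tailed at 0.05, with counts of individually better, unchanged and worse subjects reported beside it. A conclusion reached that way would be sound.

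The remaining freedom, paired t-test or signed-ranks test, is worth about 1.5 points of power at 23 evaluable subjects, and reporting both would make the choice visible. Restating the level or relabelling the binomial comparison would change no result.

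This rests on two assumptions: that section 10.1 remains in force, since nothing in the SAP withdraws it, and, for the power figures, a standardised change of 0.7075 with normally distributed differences. The timing of the test choice cannot be judged from the documents.
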